#### REASONABLE POSSIBILITY

- The AE follows or may follow a reasonable temporal sequence from PDT-Photofrin® administration;
- The AE disappears or abates upon discontinuation of PDT-Photofrin® (dechallenge) and/or reappears or worsens on repeated exposure (rechallenge);
- The AE cannot be reasonably explained by known characteristics of the subject's clinical state, history, environment, other therapy administered to the subject (drug or non-drug); and/or
- The AE is a known effect of PDT-Photofrin®.

### 8.4.3. Reporting Requirements

#### **8.4.3.1. Serious Adverse Events**

All SAEs, regardless of relationship to study treatment, must be reported by the investigator to the sponsor-designated third party drug safety group (Mapi Group, UK), by completing the SAE form within 24 hours of awareness. This includes SAEs occurring as soon as the subject signs the informed consent (i.e., pre-treatment SAEs). Serious Adverse Events which could be associated with the study procedures and which could modify the conduct of the study are reportable within 24 hours. In addition, any spontaneously reported SAE that occurs within 30 days after the last study procedure for subjects who completed the study protocol or within 90 days after the Photofrin® injection for subjects who prematurely discontinued study treatment should be reported using the SAE form.

The SAE form should be completed as thoroughly as possible, given the information available and time constraints. Upon completion, the SAE form should be signed by the investigator or sub-investigator and faxed or emailed to the designated drug safety group.

Conventional paper-based SAE Form will be provided in the Investigator Study File (ISF). The form will also be electronically available.

Death and surgery should not be reported as an event. Death and surgery are viewed as an outcome of an event, rather than the event itself. In cases where the cause of death is unknown, death may be initially reported as an event. Every attempt should be made to submit a follow-up report identifying the cause of death.

All SAEs will be monitored by Concordia Laboratories Inc. or designee in real time throughout the study.

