#### 3.2. Scheduling of Visits

Pretreatment assessments will be performed during the 30 days prior to enrollment. After enrollment, study visits will be as follows:

- Study Day 0 will be the day the subject is enrolled.
- Study Day 1 will be the day of the PHO injection. Study Hour 0 will be the time of the end of PHO injection.
- Study Day 3 will be the day of PDT. Study Hour 40-50 will be calculated from Study Hour 0.
- Study Day 13 to Day 18 will be the time-period where the surgery will be performed post PDT.

- 
- Study Day 20 to Day 25 ( $\pm 2$  days) will be the 7-day post-surgery visit.
  - Study Day 43 to Day 48 ( $\pm 3$  days) will be the 30-day post-surgery visit.
  - Study Day 103 to Day 108 ( $\pm 7$  days) will be the 90-day post-surgery last study visit.

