#### 4.7. Early Discontinuation Criteria

Early discontinuation from study will not, on its own, invalidate a subject for the safety analyses.

An investigator may choose to remove a subject from the study for any variety of reasons. Below is a list of possible reasons for removal of a subject; however, it does not include all possible justifiable reasons for removing a subject from the study.

1. The subject has been included in violation of the inclusion / exclusion criteria (as described under Section 4.3).
2. The subject chooses to discontinue participation for personal reasons (e.g., moving away, no time).
3. The subject chooses to discontinue, or is discontinued by the investigator or the sponsor due to intolerable, serious or unexpected adverse event or laboratory values judged to be clinically significant.
4. The investigator or the sponsor discontinues the subject for a significant protocol violation (e.g., pregnancy, current participation in another clinical study, etc.).
5. An illness newly develops as determined by the physician in charge that compromises continued participation.
6. The subject is uncooperative or does not comply with the protocol requirements (e.g., failure to return for scheduled visits at the enrolling study site, failure to complete study evaluation tools, failure to follow instructions).

7. In the investigator's or sponsor's judgment, withdrawal from the study would be in the subject's best interest (e.g., an immediate medical or surgical procedure is required that would compromise the subject's continued participation, lack of adequate therapeutic response resulting in intolerable symptoms or unacceptable risk).
8. The study is terminated by the sponsor.

For any subject who leaves the study, the investigator must complete the CRF up to the time study participation is terminated. Every effort should be made to ascertain the reason for discontinuation and to perform the early discontinuation procedures (Section 5.3.2). All reasonable effort must be made to contact subjects who fail to return for scheduled visits and to encourage them to comply with the procedure. All attempts to contact subjects must be clearly documented. The investigator will advise the sponsor immediately of every dropout by telephone, facsimile, or E-mail.

In case of withdrawal of consent, the date of and the reason for withdrawing consent will be collected. No additional data will be collected from the time of consent withdrawal.

---

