2.2 Study Design

This is a prospective, multicenter, uncontrolled, non-randomized, open-label, clinical study with the primary objective to assess safety of PDT in subjects with peripherally located malignant tumors in lung parenchyma prior to surgical resection. A Time and Procedures Schedule for the overall conduct of the study is outlined in section 8.

The primary diagnosis will be performed as per standard of care no more than 60 days prior to consent signature. Upon signing consent, subjects will be assigned a unique participation number and will undergo screening evaluation conducted during the 30 days prior to enrollment. This phase will involve medical evaluations and thorough review of all reports that led to the primary diagnosis. Upon successful screening evaluations, subjects will be enrolled into the study.

Treatment Procedures will consist of one PDT-Photofrin® course performed through navigational bronchoscopy or peripheral ultrasound guided bronchoscopy. One course will consist of an intravenous (IV) injection of Photofrin® (PHO) 2 mg/kg over 3-5 minutes followed by one laser light application session. The end of injection will be Study Hour 0. Photodynamic laser therapy will be performed on Study Hour 40-50. Laser light (630 nm wavelength) will be applied at a dose of 200 J/cm of the diffuser length.

Ten to 15 days after PDT, subjects will undergo surgery as per standard of care. Macroscopic and microscopic examinations of the tumor and surrounding healthy lung tissue will be evaluated to determine the effect of PDT on the tumor and the healthy/non-tumor lung tissue. Macroscopic examinations will be performed at the local institution. Microscopic examinations will be performed by a central reader pathologist.

Follow-up assessments will include some or all the following procedures: physical exam; vital signs evaluation; body weight measurement; chest CT; chest X-ray; performance status; and clinical laboratory testing. All subjects will be asked general questions about the occurrence of adverse events, concurrent medical conditions, use of adjunctive therapy/procedure, and intake of concomitant medication.

Data will be analyzed to evaluate the safety of the modality up to 90 days post-surgery.

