Study Day = (Target Date - Date of the study drug administration) + 1 if target date is greater than or equal to the date of the study drug administration or

Study Day = (Target Date – Date of the study drug administration) if target date is less than date of the study drug administration.

All dates will be displayed in DD/MMM/YYYY format.

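### The SAE reporting window after early discontinuation closes on Day 91, 12 to 17 days before the 90-day post-surgery safety horizon, and does not clearly cover treated subjects who leave later

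*Protocol*

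**What the plan says.** Protocol Section 8 has AEs recorded from consent until the subject completes or discontinues. Beyond that, Protocol 8.4.3.1 keeps a passive window open for SAEs:

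- Completers: "any spontaneously reported SAE that occurs within 30 days after the last study procedure for subjects who completed the study protocol".
- Others: "within 90 days after the Photofrin" "injection for subjects who prematurely discontinued study treatment should be reported using the SAE form".

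The SAP sets the analysis horizon in 2.2: "Data will be analyzed to evaluate the safety of the modality up to 90 days post-surgery". The protocol synopsis likewise gives a follow-up of 3 months after surgery. Protocol 3.1 says only 90 days, without naming the starting point.

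A subject who leaves for a reason other than consent withdrawal has one discontinuation assessment (Protocol 5.3.2.2) and no scheduled visits after it. After consent withdrawal nothing more is collected (5.3.2.1). SAEs already known are followed until resolved or judged acceptable (8.5). The same section keeps follow-up information that arrives after the last study procedure out of the CRF and sends it to the sponsor on the SAE form.

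For the analysis, the Safety Population is every enrolled subject who received the injection (SAP 5.2.2). AE results are numbers and percentages of subjects, with exact one-sided upper limits (SAP 5.4.11.1).

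**The concern.** The two windows have different anchors, one the last study procedure and the other the injection. The injection-anchored window stops before the date to which the SAP says safety is evaluated. It is also worded around discontinuing study treatment, which is one injection and one light session and is finished by Day 3. It is therefore unclear which window, if either, applies to someone who was fully treated and left the study afterwards.

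This bears on the primary endpoint, which includes SAE incidence (SAP 4.1). The percentages are crude. A subject who leaves early stays in the denominator, and any unobserved time up to the horizon counts in effect as event-free. Harm is among the listed reasons for leaving, since a subject may go because he or she "is discontinued by the investigator or the sponsor due to intolerable, serious or unexpected adverse event". A late SAE in such a subject is therefore a case that the plan should handle explicitly.

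**Working it through.** **Inputs.** "Study Day 1 will be the day of the PHO injection" and "Study Day 3 will be the day of PDT" (Protocol 3.2). Surgery is 10 to 15 days after PDT (Protocol 3.1). The last visit is on Day 103 to 108, ±7 days (Protocol 3.2). The SAP counts days as "Study Day = (Target Date - Date of the study drug administration) + 1 if target date is greater than or equal to" the administration date (SAP 5.1).

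**1. Reproduce the plan's own days.** Surgery: 3 + 10 = 13 and 3 + 15 = 18, so Day 13 to 18. Ninety days later: 13 + 90 = 103 and 18 + 90 = 108, so Day 103 to 108. Both match the protocol.

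**2. End of the injection-anchored window.** Day 1 + 90 = Day 91. In days after surgery this is 91 − 13 = 78 or 91 − 18 = 73. The window therefore reaches day 73 to 78 after surgery, not day 90.

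**3. Shortfall against the horizon.** 103 − 91 = 12 and 108 − 91 = 17 days. With the ±7-day visit allowance, the last visit can fall from Day 96 to Day 115, so the shortfall is 96 − 91 = 5 to 115 − 91 = 24 days. It is positive throughout.

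**4. Completers' window.** 103 + 30 = 133 and 108 + 30 = 138. It ends 133 − 91 = 42 to 138 − 91 = 47 days after Day 91. Of that difference, 30 days lie beyond the SAP horizon (42 = 12 + 30; 47 = 17 + 30). Only the 12 to 17 days in step 3 concern the planned analysis period.

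**5. Length of reporting after exit.** For a subject under the 90-day clause it is 91 minus the exit day:

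| Exit day | Days of reporting after exit |
|---|---|
| 5 | 86 |
| 18 | 73 |
| 48 | 43 |
| 61 | 30 |
| 91 or later | 0 |

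The window after exit equals the completers' 30 days at an exit on Day 61. It is longer before that day and shorter after it.

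**6. Who is covered.**

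| Subject | Window after exit on a literal reading of 8.4.3.1 |
|---|---|
| Completes the study | 30 days after last procedure |
| Injected, treatment not completed | To Day 91 |
| Injected and illuminated, leaves the study later | None stated |
| Withdraws consent | None (5.3.2.1) |

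Protocol 5.2 groups surgery and follow-up under treatment procedures. A wider reading that puts the third row under the Day 91 clause is therefore possible, but the text does not settle it.

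**7. What one event is worth.** With 10 subjects, 0/10 against 1/10 moves the exact one-sided 95% upper limit from 0.26 to 0.39 (table in Protocol 10.1). This shows the scale at N = 10. It says nothing about how likely a missed event is.

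**The case against.** An injection anchor has a real advantage: it is defined for every injected subject. A post-surgery date does not exist for someone who never has the operation, so the 12 to 17 days apply only to operated subjects. The protocol uses 90 days elsewhere for photosensitivity (7.1) and for contraception after the injection (Appendix 13-1), so the choice is coherent even though no reason is given. If the 90 days in Protocol 3.1 ran from injection, Day 91 would meet it. The first of these points stands and shapes the fix. The last is the weaker reading, because the synopsis and the SAP both count from surgery.

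A reader might infer that the subjects likeliest to be harmed are watched least. The documents do not support that. Adverse events are one of eight non-exhaustive reasons in Protocol 4.7, and no rates are given. A subject who leaves before Day 61 under the 90-day clause has a longer passive window after exit than a completer. Known SAEs are followed until resolved or judged acceptable, so the gap concerns new events only.

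A reader might also take the 42 to 47 days as the loss, or conclude that SAE incidence is biased downward by a known amount. Most of that difference lies beyond the analysis horizon. Nor do the documents say whether SAE-form reports received after exit, from anyone, enter the tables. Lengthening the window alone might therefore leave the tabulated incidence unchanged, and the SAP has to change as well.

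**Conclusion.** The point holds as a gap in coverage and wording. For subjects under the discontinuation clause, reporting of new SAEs ends on Day 91. That is 12 to 17 days before the nominal 90-day post-surgery horizon (5 to 24 with the visit allowance). A fully treated subject who leaves later has no clearly stated window. Because these subjects remain in the crude denominator, a late new SAE can go uncounted. The SAP has no rule for counting SAEs reported after exit: its treatment-emergent definition has a start but no end date.

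This assumes surgery within Day 13 to 18, the SAP's post-surgery horizon and the SAP's day convention. How much incidence is missed, and in which direction discontinuers differ from completers, cannot be worked out from the documents. It is a cheap improvement and not a threat to the study's validity.

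**What to change.** Rewrite the sentence in Protocol 8.4.3.1 so that every injected subject who has not withdrawn consent has SAEs reported at least to 90 days after surgery. If no surgery takes place, use an equivalent named study day, for example Day 108, the end of the nominal last-visit range. Word it by leaving the study as well as by stopping treatment, so that no treated subject falls between the clauses. State the starting point of the 90 days in Protocol 3.1.

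Add to SAP 5.4.11.1 that SAEs with onset in this common window count in the SAE tables whatever the discontinuation status, including those reported on the SAE form after exit. Reconcile this with Protocol 8.5, so that the information needed for the tables reaches the analysis data.

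The cost is an occasional extra SAE report and a step to bring SAE-form reports into the analysis dataset. No visits are added.

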#### **8.4.3.2. Adverse Events**

All AEs will be reported on the Adverse Events Form of the CRF.

#### **8.4.3.3. Pregnancy**

Pregnancy will be recorded and reported within 24 hours to the sponsor designee. Any pregnancy that occurs to study subjects or their partners during the study should be recorded and reported using the appropriate pregnancy surveillance form provided in the ISF. Pregnancy's outcome should also be reported. When the newborn is healthy, additional follow-up is not needed. In case of health problem in the newborn, follow-up must be performed and the investigator will provide follow-up information concerning the outcome of pregnancy within 24 hours of awareness.

#### **8.4.3.4. Other Reportable Events**

The following should be recorded and reported on the appropriate form provided in the ISF:

- Drug abuse and overdose with or without AEs. An overdose is a dose higher than that prescribed by a health care professional for clinical reasons. It is up to the participating investigator to decide whether a dose was an overdose;
- Inadvertent or accidental exposure to Photofrin® with or without an AE;
- Any other medication errors (including dispensing errors such as inadvertent use of expired medication and dosing errors) with or without an AE;
- Suspected transmission of an infectious agent.

### **8.5. Follow-Up and Final reports**

The clinical condition of subjects who have had a SAE must be followed until all parameters, including laboratory values, have either returned to normal or to baseline value or are otherwise explained or judged acceptable by the investigator. Follow-up and/or Final Reports, including information on the action taken and the outcome, must be sent to the sponsor.

In the event of death, any post-mortem findings (including histopathology and an autopsy report) must be provided to the sponsor.

If the follow-up information is received after the last study procedure or last Photofrin® administration, this information will not be recorded in the CRF but should be provided to the sponsor using the SAE form provided in the ISF.

---

#### 8.6. Data Safety Monitoring Board

A Data Safety Monitoring Board (DSMB) will be formed of three experts (two clinicians and one statistician) all of whom are independent of the sponsor and the investigators conducting the study. The DSMB will independently review safety data and, if needed, recommend any changes to the conduct of the study for safety reasons. The DSMB will also review the final analyses.

#### 8.7. Regulatory Aspects

Concordia Laboratories Inc. has a legal responsibility to notify the Health Products and Food Branch (HPFB) of Canada, the FDA of the USA, European Medicines Agency (EMA), National Competent Authorities and Central Ethics Committees of European Union, and all other foreign regulatory agencies as well as all study sites about the safety of Photofrin®.

The investigator has the responsibility to notify the local Ethics Committee about SAEs. Copies of the notification to the ethics committee must be sent to the sponsor.

## 9. UNANTICIPATED PROBLEMS

### 9.1. Definition

An unanticipated problem is defined as any occurrence that may negatively affect the subject and/or the study conduct and that is not in accordance with the approved study documents. The unanticipated problem can be related to a specific subject or to the whole site.

### 9.2. Categories of Unanticipated Problems

Unanticipated problems should be classified in at least one of these categories:

Categories of Unanticipated problems

Risk	Definition	Example
Physical risk	Unanticipated problem that may jeopardize the physical health of the subject.	Potential physical hazard associated with the participation of subject(s) to the study such as building refection and/or use of dysfunctional medical material.
Psychological risk	Unanticipated problem that may jeopardize the psychological health of the subject.	Pressure coming from another health professional and/or subject(s) relative regarding the participation of subject(s) to the study.
Economic risk	Unanticipated problem that may negatively impair the economic status of the subject.	Unplanned financial burden for subject(s) due to loss of income or expenses related to the study conduct (e.g., travelling to another site for a study procedure, etc.)
Social risk	Unanticipated problem that may negatively impair the social behavior of the subject.	More frequent and/or unplanned follow-up visit(s) and/or procedure(s) affecting subject(s) social life.
Other	Unanticipated problem that may represent a risk to the subject (other than physical, psychological, economic and/or social) or that may jeopardize the study conduct.	Partial or total loss of subject(s) confidential information.

### 9.3. Reporting of Unanticipated Problems

Unanticipated problems identified during the course of the clinical study should be reported to the sponsor within 24 hours of awareness using the appropriate form of the CRF. Occurrences meeting the definition of adverse event (see Section 8.1) should be reported as an adverse event (Adverse Event form of the CRF) and not as unanticipated problem. For site-related unanticipated problem, the data will be entered under only one subject and will be identified as site-specific on the unanticipated problem form of the CRF.

## 10. DATA MANAGEMENT AND STATISTICS

### 10.1. Sample Size/Power Considerations

This study is designed to assess the safety of PDT in subjects with solid lung tumors prior to surgical resection and to assess the lung tumor and healthy tissue response to PDT. The intent of this study is to enroll 10 subjects. This sample size has the following precision for estimation of rates of AE's of special interest (AESI). The following table shows historical AE rates for RFA ranging from <1 to ~50%.

AESI	Rate observed with RFA
Pneumothorax	11-52%
Pleural effusion	6-19%
Hemorrhage	6-18%
Pulmonary artery pseudoaneurysm	0.2%
Needle tract seeding	0.3-0.7%
Cavitation	14%
Bronchopleural fistula	0.6%
Pneumonitis	0.4%

The sample size of N=10 has precision for estimation of AE rates for estimates ranging from <0.01 to ~0.5 as shown in the following list. Precision is measured by 1-sided 95% upper confidence limit (CL) on the estimated AE rate *via* exact binomial distribution. PDT is expected to have lower AE rates than RFA, so, for example, for a RFA historical rate of 0.27 (27%), if no such AE's are observed on PDT, then the TRUE underlying PDT rate is lower than 0.27 with 95% confidence since the upper 95% CL is 0.26 - indicated by "\*" in the list below.

No. of AESIs	Rate	Upper 1-sided 95% confidence limit
0	0.00	0.26*
1	0.10	0.39
2	0.20	0.51
3	0.30	0.61
4	0.40	0.70
5	0.50	0.78

The study will be suspended and re-evaluated from a safety standpoint if 20% of the subjects experience a serious adverse event that is related to PDT.

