### 3. STUDY DESCRIPTION

#### 3.1. Over all Study Description

This is a prospective, multicenter, uncontrolled, non-randomized, open-label, clinical study with the primary objective to assess safety of PDT in subjects with peripherally located malignant tumors in lung parenchyma prior to surgical resection. A Time and Procedures Schedule for the overall conduct of the study is outlined in Appendix 13-1.

The primary diagnosis will be performed as per standard of care no more than 60 days prior to consent signature. Upon signing consent, subjects will be assigned a unique participation number and will undergo screening evaluation conducted during the 30 days prior to enrollment. This phase will involve medical evaluations and thorough review of all reports that led to the primary diagnosis. Upon successful screening evaluations, subjects will be enrolled into the study.

Treatment Procedures will consist of one PDT-Photofrin® course performed through navigational bronchoscopy or peripheral ultrasound guided bronchoscopy. One course will consist of an intravenous (IV) injection of Photofrin® 2 mg/kg over 3-5 minutes followed by one laser light application. The end of injection will be Study Hour 0. Photodynamic laser therapy will be performed on Study Hour 40-50. Laser light (630 nm wavelength) will be applied at a dose of 200 J/cm of the diffuser length.

Ten to 15 days after PDT, subjects will undergo surgery as per standard of care. Macroscopic and microscopic examinations of the tumor and surrounding healthy lung tissue will be evaluated to determine the effect of PDT on the tumor and the healthy/non-tumor lung tissue. Macroscopic examinations will be performed at the local institution. Microscopic examinations will be performed by a central reader pathologist.

Follow-up assessments will include some or all the following procedures: physical exam; vital signs evaluation; body weight measurement; chest CT; chest X-ray; performance status; and clinical laboratory testing. All subjects will be asked general questions about the occurrence of adverse events, concurrent medical conditions, use of adjunctive therapy/procedure, and intake of concomitant medication.

Data will be analyzed to evaluate the safety of the modality up to 90 days.

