### 4.2. Number of Subjects

This study plans to enroll up to approximately 10 subjects from about five US clinical research sites experienced in navigational bronchoscopy.

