##### 10.5.3. Safety Analysis

Safety analysis will be performed on the Safety Population.

The number and percentage of subjects with normal and abnormal findings will be provided for each physical examination in a shift table comparing screening and the end of study evaluation.

Vital signs will be summarized descriptively (mean, standard deviation, median, minimum and maximum). Change from baseline will also be summarized.

Skin photosensitivity is an adverse event of special interest and will be summarized separately from other adverse events at each safety assessment. Changes in skin will be assessed by grade of erythema, edema and blistering. The data will be tabulated by CTCAE grade in the Dermatology/Skin category.

Descriptive statistics for each clinical laboratory test will be presented for the baseline and the end of study assessment. Change from baseline will also be summarized. According to the laboratory normal ranges, laboratory test results will be categorized as low (< lower limit of normal, LLN), normal (within normal range), and high (> ULN). Shift tables, comparing the distributions of these three categories at baseline versus the end of study assessment, will be presented.

---

Concomitant medications will be coded using the WHO Drug dictionary. Medications initiated prior to start of treatment and maintained during the study, or taken during the course of the study will be considered as concomitant medications. Concomitant medications will be summarized according to the preferred terms only.

Adverse events will be coded using the Medical Dictionary for Regulatory Activities (MedDRA). The number and percentage of subjects who experienced any AEs as well as serious AEs will be presented by system organ class (SOC) and by preferred term (PT) within SOC. All AEs will be similarly presented by intensity (mild, moderate, severe or using the CTCAE grading system) and by relationship to treatment (reasonable possibility/no reasonable possibility). One-sided 95% confidence limit will be computed for each AE percentage via exact binomial method (Clopper-Pearson, 1934).

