5.4.11.1 Adverse Events

Adverse Events will be coded using the Medical Dictionary of Regulatory Activities (MedDRA version 20.0) AE coding system for purpose of summarization.

Events collected at the "NCS Events" CRF page will be summarized together with Adverse Events, but excluded from analyses by CTCAE grade and relationship to study drug, since these data points are not captured for NCS events.

An AE will be defined as treatment-emergent (TEAE) if its date of onset is on or after the date of the study drug (PHO) administration.

An AE will be defined as treatment-related if its relationship to the study drug is recorded as "Reasonable Possibility" on the CRF.

An overall summary of number and percentage of subjects with at least one AE, TEAE, serious TEAE, treatment-related TEAE, serious treatment-related TEAE, TEAE leading to discontinuation and fatal TEAE will be presented.

A summary of the frequency (number and percentage of subjects) of TEAEs will be presented by system organ class and preferred term. One-sided 95% upper confidence limit will be computed for each AE percentage via exact (Clopper-Pearson) method for binomial proportion. Adverse events will also be analyzed by their CTCAE grade (1 to 5) and relationship to study drug (related or not related).

A subject experiencing the same AE multiple times will be counted only once for that preferred term. Similarly, if a subject experiences multiple AEs (preferred terms) within the same system organ class, then that subject will be counted only once for that system organ class. When summarizing by CTCAE grade and relationship, only event with highest grade or relationship will be counted. All AEs will be presented in alphabetical order of SOC and preferred terms.

Skin photosensitivity is an adverse event of special interest (AESI). Skin photosensitivity will be summarized separately by SOC and preferred term as well as by SOC, preferred term and CTCAE grade.

All information pertaining to adverse events noted during the study will be listed by subject, detailing verbatim term given by the investigator, preferred term, system organ class, start date, stop date, CTCAE grade, outcome, action taken and drug relatedness. Separate listings will be created for Serious TEAEs, TEAEs leading to study drug discontinuation and skin photosensitivity events.

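### Does the sample-size section claim more precision from 10 subjects than the exact limits can deliver?

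*Protocol*

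**What the plan says.** Protocol 10.1 gives the rationale for 10 subjects, and SAP 3.1 repeats it. The section first says that the sample size provides the precision it is about to set out. It then introduces a table of eight events: "The following table shows historical AE rates for RFA ranging from <1 to ~50" percent. Next comes "The sample size of N=10 has precision for estimation of AE rates for estimates ranging from <0.01 to ~0.5 as shown in the following list", followed at once by the yardstick: "Precision is measured by 1-sided 95% upper confidence limit (CL) on the estimated AE rate", by the exact binomial distribution. The list shows 0 to 5 events, observed rates of 0.00 to 0.50, and upper limits of 0.26, 0.39, 0.51, 0.61, 0.70 and 0.78. One illustration is worked: "for a RFA historical rate of 0.27 (27%), if no such AE's are observed on PDT", the true rate is taken to be below 0.27 because the limit is 0.26. That row carries a star.

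The analysis sections use the same measure. Protocol 10.5.3: "One-sided 95% confidence limit will be computed for each AE percentage via exact binomial method". SAP 5.4.11.1: "One-sided 95% upper confidence limit will be computed for each AE percentage via exact (Clopper-Pearson) method for binomial proportion". Protocol 3.1 describes the design: "This is a prospective, multicenter, uncontrolled, non-randomized, open-label, clinical study". Protocol 4.2 gives only a count: "This study plans to enroll up to approximately 10 subjects".

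**The concern.** The range below 0.01 to about 0.5 is the RFA range restated as proportions, and the text goes on to say that lower rates are expected with photodynamic therapy than with RFA. Read in that sequence, the sentence seems to promise useful precision across all eight RFA rates. With 10 subjects that would be untrue. The lowest attainable limit is about 26%, while four of the listed RFA rates are below 1% and three more have tops of 14% to 19%. The 27% illustration falls inside only one listed range, pneumothorax (11-52%), and the text does not name the event.

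This section is the only justification for N in either document. If it did overstate, a reader might take an event-free result as evidence of improvement on RFA for events where 10 subjects can show no such thing.

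**Working it through.** **Inputs.** N = 10, the one-sided 95% exact upper limit, the six printed limits and the eight RFA rates, all from Protocol 10.1 and SAP 3.1.

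**1. Reproduce the printed limits.** The Clopper-Pearson one-sided upper limit for x events in n subjects is the 0.95 quantile of Beta(x + 1, n − x). For x = 0 it reduces to 1 − 0.05^(1/n).

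| Events of 10 | Computed limit | Printed |
|---|---|---|
| 0 | 0.2589 | 0.26 |
| 1 | 0.3942 | 0.39 |
| 2 | 0.5069 | 0.51 |
| 3 | 0.6066 | 0.61 |
| 4 | 0.6965 | 0.70 |
| 5 | 0.7776 | 0.78 |

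All six agree. A two-sided 95% interval would give 0.3085 at zero events, so the plan used the one-sided version it names.

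**2. Check the worked example.** 0.2589 < 0.27. Equivalently, the chance of no events in 10 at a true rate of 27% is (1 − 0.27)^10 = 0.043, below 0.05. The example is right.

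**3. Set the smallest limit against the RFA table.** The last column is (1 − r)^10, where r is the top listed RFA rate.

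| Event | Top RFA rate r | Is 0.2589 above r? | Chance of 0/10 at r |
|---|---|---|---|
| Pneumothorax | 52% | no | 0.0006 |
| Pleural effusion | 19% | yes | 0.122 |
| Hemorrhage | 18% | yes | 0.137 |
| Cavitation | 14% | yes | 0.221 |
| Needle tract seeding | 0.7% | yes | 0.932 |
| Bronchopleural fistula | 0.6% | yes | 0.942 |
| Pneumonitis | 0.4% | yes | 0.961 |
| Pulmonary artery pseudoaneurysm | 0.2% | yes | 0.980 |

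So the factual core of the concern is correct: for seven of eight events no possible result in 10 subjects puts the limit below the RFA rate.

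**4. Ask what the sentence asserts.**

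- Its subject is estimates, that is, observed proportions. With N = 10 these move in steps of 0.10, and the list covers 0.00 to 0.50. The only attainable estimate below 0.01 is 0/10, which is the first row.
- It refers the reader to the list for the precision itself, in line with the section's opening statement. It gives the size of the precision and does not call it adequate.
- The next sentence defines precision as the upper limit, and each row has one. At the bottom of the range the stated precision is 0.26, so the reader is told how wide it is.
- Nowhere does the section say that the limit will fall below each RFA rate. The one comparison made uses a stated reference of 27% and is offered as an example.

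**5. Ask whether anything depends on it.** Protocol 10.5 and SAP 5.4 contain no comparison with RFA. They report counts, percentages and an exact upper limit for each adverse event. The only event singled out for separate safety summaries is skin photosensitivity, which is not in the RFA table.

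**The case for a change.** The best case for the concern is that the match between the two ranges is unlikely to be chance. A lower end of below 0.01 is an odd description of a column that starts at exactly 0.00 and next steps to 0.10, but it fits the RFA rates well. The surrounding text is comparative, and the single example happens to be favourable: even within pneumothorax, zero events in 10 could not exclude the 11% end of the range, where the chance of that result is (1 − 0.11)^10 = 0.312. On this view the sentence should say outright that seven of the eight events are out of reach.

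Part of this stands. The phrasing is loose, zero would have been a cleaner lower end, and the example could have named its event, though the documents attribute 27% to none. But an echo of the RFA range is not a claim about it, and the information needed to avoid a misreading is not withheld. The RFA rates and the 0.26 limit are in neighbouring tables, and anyone comparing them sees that 0.26 exceeds 19%, 18%, 14% and everything below 1%. The supposed harm requires a reader to ignore the starred row. The much larger samples needed to bring a zero-event limit below the rarest rates (1497 for 0.2%) have no bearing on a descriptive Phase Ib study of about 10 subjects.

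**Conclusion.** There is no error here. The limits and the worked example are correct, and the sentence is true when read with the definition and list that follow it. The limited reach of 10 subjects is real: 0.259 is 1.36 times the top RFA rate for effusion (0.2589 / 0.19), 1.85 times that for cavitation (0.2589 / 0.14), and far above the rates below 1%. It is also disclosed in the plan's own figures. An explicit caveat would be a matter of editorial taste and would leave N, the table, the analyses and the conclusions as they are.

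This rests on two things. First, the safety analysis stays descriptive, as both documents state; a formal claim against RFA for the seven events would be unsupported. Second, the illustration is tied to N = 10. If only 9 subjects were treated, the zero-event limit would be 1 − 0.05^(1/9) = 0.283 and the 27% example would no longer apply. The section states it for 10 and does not extend it.
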